8.3 Treatment Schedule

The treatment period is divided into cycles. Each cycle in Q3W dosing lasts three weeks (21 days). The IMP will be administered on Day 1 of each cycle (Q3W) for up to one year with the possibility to extend the treatment beyond one year according to routine clinical practice (see [Section 8.7.1](#)). If the IMP infusion cannot be administered as scheduled the IMP infusion must be administered as soon as possible. The IMP administration day is counted as Day 1 of the cycle (for delays see [Section 8.7](#)).

Protocol Addendum implements more frequent dosings (Q2W and Q1W). Protocol Addendum requires all relevant national approvals in the countries concerned prior to implementation.

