8.4 Assessments during Treatment Period

The assessments during the trial are described in the following chapters and also in [Table 1](#) (Part I), [Table 2](#) (Part II) and [Table 3](#) (Part III). Before each IMP administration, a pre-dose physical evaluation is conducted. AEs will be collected during the whole treatment period starting after the signing of the Informed Consent.

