8.7.1 Treatment beyond One Year

In case that, as judged by the investigator, it would be beneficial to continue the treatment beyond one year, the protocol allows the treatment according to normal clinical practice, in order to allow the treatment continuation of the study subjects, provided that the clinical development and manufacturing of FP-1305 continues and it is not available via other routes. If the treatment is continued beyond one year, the following procedures/assessments will be done:

- FP-1305 infusion every three weeks
- Collection of weight, vital signs, physical examinations, ECOG, CBC, and CMP pre-dose for every infusion during the second year of treatment
- All available clinical routine images will be utilized. 18- (\pm 1 month) and 24- (\pm 1 month) month images from the first dose are mandatory to take if not routinely taken at these timepoints
- Collection of treatment related adverse events
- Collection of survival data (limited to 1 year from the last IMP dose if the treatment has been continued beyond one year)

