8.7.2 Treatment Hold in Complete Response

If a study subject meets the irRECIST criteria for a confirmed complete response, the treatment can be placed on hold. The subject should complete follow-up visit but continues in the trial without treatment (FP-1305). Surveillance is conducted using routine good medical care and the results with AE evaluation will be reported to the Sponsor. The treatment with FP-1305 can be continued if the disease progresses (Trial duration and Treatment extension beyond one year definitions shall apply) and the trial is still ongoing. The decision of re-initiation must be agreed between the investigator, the Medical Monitor and the Sponsor and carefully documented to justify the decision. A written informed consent for treatment re-initiation will be obtained before the treatment can be started. The subject will enter to the study using the same subject number as before discontinuation. Relevant medical data received post study completion/ discontinuation will be collected in the eCRF once the subject has given the written consent for the re-initiation. The following pre-dose assessments will be performed prior to the re-initiation:

- CT/MRI scan
- ADA
- Vital signs, physical examinations, ECOG, CBC, and CMP

Once the treatment has been reinitiated, 'Treatment Beyond One Year' procedures will apply to each cycle. Tumour imaging will be performed at 2, 4, 6, 9, 12, 18 and 24 months timepoints after re-initiation of the treatment and ADA will be collected at the end of the treatment and if clinically indicated. The subject will receive the dose used in the study at the time of the re-initiation, even if the subject was previously on another dose. Once it has been decided that a subject will permanently stop treatment, a Follow-up Visit should be performed 4 weeks (+/- 1 week) after their last dose of IMP. If the last IMP dose was >5 weeks at the time of the decision, the Follow-up Visit should be performed as soon as possible.

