11.3 Adverse Events

It is the responsibility of the Investigator to collect all AEs (both serious and non-serious) derived by observation, by spontaneous unsolicited reports of subjects, and, where appropriate, by routine open questioning.

As this is a first in human trial, all medical occurrences which meet the definition of an AE ([Section 5](#)) should be recorded. Disease progression will be recorded as an AE/SAE in this study.

Any **pre-existing conditions** or abnormal laboratory findings present at screening should be recorded in the medical history and should not be recorded as an AE unless the condition worsens by at least one CTC grade during the trial.

Abnormal laboratory findings (e.g., biochemistry, haematology, urinalysis) or other abnormal assessments (e.g., vital signs) that are judged by the Investigator as clinically significant will, if certain requirements are met, be recorded as AEs or SAEs. Clinically significant abnormal laboratory findings or other abnormal assessments that meet the definition of an AE or SAE and are detected during the study or are present at screening and significantly worsen following the start of the study, will be recorded as AEs or SAEs. However, clinically significant abnormal laboratory findings or other abnormal assessments that are associated with the disease being studied (unless judged by the Investigator as more severe than expected for the subject's condition), or that are present or detected at the start of the study and do not worsen, will not be recorded as AEs or SAEs. The Investigator will exercise their medical and scientific judgment in deciding whether an abnormal laboratory finding, or other abnormal assessment is clinically significant.

The Investigator should assess the seriousness and causality (relatedness to the study medication) of all AEs experienced by the subject and this should be documented in the source data. The trial site is responsible for providing full details of AEs/SAEs in the electronic data capture system in the designated eCRF forms continuously during the trial.

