11.5 Adverse Events of Special Interest

Potential autoimmunity has been reported in study subjects after receiving FP-1305. Four study subjects have had hepatic involvement, with a different clinical presentation and associated AE reporting terminology. Some of these events have been graded life-threatening (more details provided in the IB).

An Adverse Event of Special Interest (AESI) is an AE that requires reporting on an expedited basis (The Investigator must report AEs that meet the definition of an AESI immediately, or within 24 hours of the trial site becoming aware of the AESI to Simbec-Orion Pharmacovigilance and on the eCRF), regardless of the seriousness, expectedness, or relatedness of the AE to the administration of the IMP.

In this protocol, the below listed are considered AESIs for FP-1305:

1. Drug induced liver injury defined by Hy's law as:
 - Grade ≥ 2 alanine aminotransferase (ALT) or aspartate transaminase (AST) increase accompanied with
 - Bilirubin elevation $> 2 \times$ upper limit of normal (ULN) if baseline value was normal; $> 2 \times$ baseline if baseline value was abnormal, without findings of cholestasis or any other reason explaining the combination of increased aminotransferase and serum total bilirubin
2. Any new or worsening of existing autoimmunity after the administration of FP-1305

All AESIs will be followed until recovery or resolution or until the investigator assesses the event to be stable. AESIs will follow the same reporting timeline as that of SAE to pharmacovigilance team.

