11.6 AE/SAE Recording and Reporting Period

Details of all AEs will be recorded from the date of consent until the AEs have resolved or no change in the AE status is observed during the post-treatment follow-up period (until Follow-up Visit has been conducted). In circumstances where follow-up visit will not be performed, the follow-up period for AE reporting is 4 weeks from last dose of IMP. If the subject is discontinued from the treatment, the subject must be followed up for open AEs until the AE has resolved, or no change in subject status is observed over the follow-up period. However, all IMP related Grade 3 or 4 AEs must be followed until resolution to Grade 2 or better (for grading see [Section 11.3.1](#)).

The investigator is not required to actively monitor subjects for adverse events occurring after the Follow-up Visit has been conducted; however, serious adverse drug reactions occurring after the follow-up period to a subject that has received one or more doses of the IMP should be reported to the Sponsor per the standard SAE reporting process (see [Section 11.4](#)) within 24 hours of the investigator or site team member becoming aware of them.

Concomitant medications and procedures associated with Serious Adverse Drug Reactions that occur after subject has withdrawn/discontinued (i.e. after Follow-up Visit) will only be recorded in SAE narrative, and not in the other eCRF pages.

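### For treatment beyond one year and after re-initiation, Protocol 8.7.1 names treatment-related events as its only AE item, while 8.4, section 11 and Tables 1 and 2 set no causality limit, and no text says which governs

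*Protocol*

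**What the plan says.** Protocol 8.7.1 opens its list prescriptively: "If the treatment is continued beyond one year, the following procedures/assessments will be done". The only entry about adverse events is "Collection of treatment related adverse events". Section 8.7.2, on restarting after a hold for complete response, says that the beyond-one-year "procedures will apply to each cycle".

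Elsewhere the protocol asks for more:

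- Section 8.4: "AEs will be collected during the whole treatment period starting after the signing of the Informed Consent".
- Section 8.3 places the extension inside the treatment schedule: dosing is "for up to one year with the possibility to extend the treatment beyond one year according to routine clinical practice".
- Section 11.3 makes the investigator responsible for collecting every AE, serious or not, and gives the first-in-human status of the trial as the reason for recording everything that meets the AE definition.
- Section 11.6: "Details of all AEs will be recorded from the date of consent", continuing to the Follow-up Visit, with no cut at one year and no causality condition.
- Tables 1 and 2 mark AE assessment in the beyond-one-year column without restriction.

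Two reporting streams are independent of causality. Section 11.4 requires SAEs within 24 hours, and section 11.5 requires AESIs "regardless of the seriousness, expectedness, or relatedness of the AE to the administration of the IMP".

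The Part II SAP, section 14.1, defines a TEAE as an AE that starts or worsens after at least one dose, with no upper time limit. It tabulates TEAEs by causality and severity, among other factors, and pools Part I and Part II AEs by dose.

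**The concern.** A site treating a subject in month 14, or restarting a subject after a hold, has two instructions. One asks for related events; the other asks for all events. Neither refers to the other, so two careful sites could act differently and each claim to follow the protocol.

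Safety is a primary outcome in Part II. If some late subject-time is collected in full and some only for related events, the SAP's TEAE tables put both together without marking them. TEAE totals and the not-related counts would then be too low for the restricted time, and later review of causality would have fewer events in the trial database to work with. After re-initiation the narrower wording would apply from the first restarted infusion, possibly at a dose different from the one the subject had before.

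**Working it through.** No figure in the documents bears on this point, so the check is of wording.

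**Step 1. Scope of AE collection, text by text**

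| Place | Period | Causality limit |
|---|---|---|
| Protocol 8.4 | whole treatment period | none |
| Protocol 11.3 | not limited | none |
| Protocol 11.6 | consent to Follow-up Visit | none |
| Protocol Tables 1 and 2 | includes beyond one year | none |
| Protocol 11.1 | 4 weeks (± 1 week) after last dose | none; no exceptions allowed |
| Protocol 8.7.1 | beyond one year | related events named |
| Protocol 8.7.2 | each cycle after re-initiation | as 8.7.1 |
| SAP Part II 14.1 | any time after first dose | none |

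**Step 2. Do the periods overlap?** Yes. Section 8.3 counts the extension as part of the treatment schedule, so the whole treatment period in 8.4 includes the time governed by 8.7.1.

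**Step 3. Is 8.7.1 a declared exception?** No. Neither 8.7.1 nor section 11 says so, and no order of precedence is given. Read literally, an unrelated event would be left out while the subject is on drug after one year, yet collected without exception in the four weeks after the last dose.

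**Step 4. Which events could be lost at a site that follows 8.7.1?**

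- SAEs are kept under 11.4.
- AESIs are kept under 11.5. They are liver injury meeting Hy's law and any new or worsening autoimmunity.
- Possibly and probably related events are kept. Under 11.3.2, an event explained equally well by another cause is possibly related.
- What remains is the non-serious, non-AESI event judged not related.

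**Step 5. Which outputs are touched?** TEAE totals, the not-related rows and the severity tables can be affected. The related-event rows, serious TEAEs and AESI listing are not. Two other Part II primary measures are also untouched: DLTs are assessed over 28 days, and response uses images obtained by Cycle 7, which starts 6 × 21 = 126 days after the first dose on the Q3W schedule if no dose is delayed.

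**The case against.** The best defence is that 8.7.1 never uses the word only and never claims to override section 11. A site reading the protocol as a whole, including Tables 1 and 2, has more text pointing to full collection than against it. Section 8.7.1 also describes continuation under normal clinical practice, where lighter data collection can be a reasonable choice.

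Part of this stands. The restriction is inferred from a prescriptive list with one AE item, and the loss arises only where a site acts on that reading. The argument does not remove the conflict: a deliberate reduction would have to be declared, and 8.4, 11.3, 11.6 and the tables leave no room for it.

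A reader might also infer more than the documents support:

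- **That any late event judged unrelated is never recorded, so a hepatic or autoimmune signal would be missed.** Sections 11.4 and 11.5 keep SAEs and AESIs whatever the causality, and the AESIs largely cover that signal. Section 11.3 also has the seriousness and causality of all AEs documented in source data.
- **That late incidence is understated 2- to 5-fold.** This takes the factor 1/(1 − s) with s, the share of events judged unrelated, assumed to be 0.5 to 0.8: 1/0.5 = 2 and 1/0.2 = 5. The documents give no value for s, the formula treats SAEs and AESIs as filtered, and the Part II SAP plans frequency and subject-count tables, not exposure-adjusted rates.
- **That safety on rechallenge is the main casualty.** Re-initiation follows a hold that requires a confirmed complete response, and section 12.1 of the Part II SAP mentions a single partial response so far. The group may be empty.
- **That the protocol expects immune events after one year.** Section 8.8 describes checkpoint-inhibitor experience and means weeks to months by late onset.

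**Conclusion.** The conflict is real and should be resolved. It is a contradiction between instructions, not a missing detail, because a site that follows 8.7.1 would leave out events that 8.4 and section 11 require and that the Part II TEAE definition counts.

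Its reach is limited. The loss concerns non-serious, non-AESI events judged not related, beyond one year or after re-initiation, at sites that act on 8.7.1. The effect on analysis is a mix of full and restricted collection in the TEAE totals and not-related counts, possibly differing between sites. The number of subjects treated beyond one year is not given; it is probably small, and that is a judgement, not a figure from the documents. No size of under-recording can be derived from them.

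The conclusion assumes that no other instruction to sites, such as eCRF completion guidance, already settles the matter. The protocol and SAP do not mention one.

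**What to change.** Replace the AE item in 8.7.1 with collection of all AEs, SAEs and AESIs as in section 11, and state in 8.7.2 that the same applies to every cycle after re-initiation. In the Part II TEAE tables, flag by footnote or indicator any subject-time already collected under the related-only wording, so that late totals and not-related counts are not read as complete.

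The cost is one line in 8.7.1, a short addition to 8.7.2 and a table flag, plus a small amount of extra AE entry. These subjects are already seen at each infusion for weight, vital signs, physical examination and laboratory tests. No dose or treatment rule changes.

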8.7.2 Treatment Hold in Complete Response

If a study subject meets the irRECIST criteria for a confirmed complete response, the treatment can be placed on hold. The subject should complete follow-up visit but continues in the trial without treatment (FP-1305). Surveillance is conducted using routine good medical care and the results with AE evaluation will be reported to the Sponsor. The treatment with FP-1305 can be continued if the disease progresses (Trial duration and Treatment extension beyond one year definitions shall apply) and the trial is still ongoing. The decision of re-initiation must be agreed between the investigator, the Medical Monitor and the Sponsor and carefully documented to justify the decision. A written informed consent for treatment re-initiation will be obtained before the treatment can be started. The subject will enter to the study using the same subject number as before discontinuation. Relevant medical data received post study completion/ discontinuation will be collected in the eCRF once the subject has given the written consent for the re-initiation. The following pre-dose assessments will be performed prior to the re-initiation:

- CT/MRI scan
- ADA
- Vital signs, physical examinations, ECOG, CBC, and CMP

Once the treatment has been reinitiated, 'Treatment Beyond One Year' procedures will apply to each cycle. Tumour imaging will be performed at 2, 4, 6, 9, 12, 18 and 24 months timepoints after re-initiation of the treatment and ADA will be collected at the end of the treatment and if clinically indicated. The subject will receive the dose used in the study at the time of the re-initiation, even if the subject was previously on another dose. Once it has been decided that a subject will permanently stop treatment, a Follow-up Visit should be performed 4 weeks (+/- 1 week) after their last dose of IMP. If the last IMP dose was >5 weeks at the time of the decision, the Follow-up Visit should be performed as soon as possible.

8.8 Possible Toxicities

There is no experience about using FP-1305 in humans. Thus, the possible toxicities are based on the mode of action (MoA) of the drug and other drugs in this class as well as on a nonclinical toxicity study conducted in monkeys. The following toxicities can be possible:

Infusion reactions: These typically develop within 30 minutes to two hours after the initiation of the drug infusion, although symptoms (headache, pruritus, throat irritation, flushing, rash, urticaria, hypertension, and pyrexia) may be delayed for up to 24 hours. Most reactions occur after the first or the second exposure to the agent, but between 10 and 30 percent occur during the subsequent treatments. In general, the likelihood of an infusion reaction declines with each subsequent course of therapy. Proper management should take place in case these types of reactions occur (see Section 8.9.1 for general advice for treatment).

Cytokine release syndrome/Cytokine storm: The cytokine-release syndrome resembles type 1 hypersensitivity reaction and may be clinically indistinguishable. The symptoms are generally mild to moderate in severity and usually occur within the first couple of hours after starting the infusion, predominantly with the first infusion. Based on the antibody properties (no complement binding activation, no Fc-gamma receptor binding) and the lack of increased cytokine release in cytokine release assay *in vitro*, rapid onset cytokine storm is not expected (see [Section 8.2.1](#) and [Section 8.9.1](#) for general advice for treatment).

Immune-related adverse events: These are dependent on the MoA properties of the used drugs. Whenever agents that potentiate the immune system activation are used, there is a possibility that the immune system also attacks the healthy tissues. The onset of these events depends on the agents used, but the most widely experience is obtained from the immune checkpoint inhibitors (CTLA-4 or PD-[L] 1 targeting agents). The symptoms typically develop relatively late (weeks to months) during the course of the agent administration. Usually they are mild to moderate in intensity. With PD-1 therapy, the incidence of severe (Grade 3 to 4) events is low. They most commonly involve the skin, the GI tract, and the endocrine organs.

Based on the MoA properties, FP-1305 is predicted to induce immune cell activation. This activation might lead to immune-related adverse reactions. Thus, special attention should be given to fever, diarrhoea, colitis, transaminase or total bilirubin elevations, signs and symptoms of nephritis, renal dysfunction, endocrinopathies, hyperglycaemia, changes in the thyroid function, or rash. Study subjects may present with fatigue, headache, mental status changes, abdominal pain, unusual bowel habits, and hypotension, or nonspecific symptoms which may resemble symptoms caused by e.g. brain metastasis or the underlying disease. However, since FP-1305 is suspected to only induce direct tumour effects, the likelihood of irAEs is expected to be low.

Tumour lysis syndrome: Tumour lysis syndrome is an oncologic emergency that develops most often in patients with non-Hodgkin's lymphoma or acute leukaemia, its frequency is increasing among patients who have tumours that used to be only rarely associated with this complication. The onset may vary, but after Rituximab (EU)/Rituxan (US) therapy it occurs after 12-24 hours of the first infusion. It occurs when tumour cells release their contents into the bloodstream, either spontaneously or in response to therapy, leading to the characteristic findings of hyperuricemia, hyperkalaemia, hyperphosphatemia, and hypocalcaemia. These electrolyte and metabolic disturbances can progress to clinical toxic effects, including renal insufficiency, cardiac arrhythmias, seizures, and death due to multiorgan failure. Hyperphosphatemia with calcium phosphate deposition and/or the precipitation of uric acid in the renal tubules can also cause acute kidney injury.

With the emergence of new effective and targeted anticancer drugs or new combinations of drugs, tumour lysis syndrome has also been observed in patients with cancers that were previously rarely associated with this complication. At least one case of tumour lysis syndrome has been observed with anti-CSF1R therapy. It is possible that also FP-1305 can cause tumour lysis syndrome because it can direct cytotoxic T-cells to kill tumour cells. FP-1305 may also impair macrophage phagocytosis function, a MoA that may predispose to tumour lysis syndrome if a massive anti-tumour effect is achieved.

Increased fibrosis in response to liver injury: Fibrosis of the liver is an excessive accumulation of scar tissue that results from ongoing inflammation and liver cell death that occurs in most types of chronic liver diseases. Nodules, abnormal spherical areas of cells, form as dying liver cells are replaced by regenerating cells. This regeneration of cells causes the liver to become hard. Fibrosis

refers to the accumulation of tough, fibrous scar tissue in the liver. Preclinical models have demonstrated that CLEVER-1 expressing endothelial cells and macrophages may remove products of oxidative stress, thereby preventing low-level continuous injury and scarring. Since FP-1305 most likely impairs this function it is possible that the risk of fibrosis of the liver may increase if a patient has a condition that induces liver injury.

